		as adjudicated by the Central Rating Committee. First episode of psychosis defined as one or more SOPS P1-P5 rated a 6 AND either a symptom is seriously disorganized or dangerous OR one of the symptoms above occurred at least one hour per day at an average frequency of four days/week over the past month. OR a new prescription or increase in dose of an ongoing antipsychotic medication. Time of onset of first episode psychosis is defined using the rater's best estimate as determined in the SOPS interview or when the patient began taking a new prescription or increased the dose of antipsychotic medication. 
• Change from baseline in everyday functional capacity as measured by Schizophrenia Cognition Rating Scale (SCoRS) total score after 24 and 52 weeks of treatment.• Change from baseline in the Tablet based Brief Assessment of Cognition (BAC App) composite T score after 52 weeks of treatment.• Change from baseline in Positive and Negative Syndrome Scale (PANSS) positive items score, negative items score, and total score after 52 weeks of treatment.
Safety criteria:	Physical examination, vital signs, laboratory tests, electrocardiogram (ECG), suicidality, extrapyramidal symptoms, and occurrence of serious and non-serious adverse events will be assessed.	
Statistical methods:	For the primary endpoint of time to remission from APS, the equality of the hazard rates will be tested by the Wald test for the treatment effect in a stratified Cox proportional hazards model at the two-sided 10% significance level. The model includes the treatment effect and	

Name of company:		Boehringer Ingelheim	
Name of finished product:		Not applicable	
Name of active ingredient:		BI 409306	
Protocol date: 09 Mar 2017	Trial number: 1289-0032		Revision date: 04 Oct 2018
categorized NAPLS risk score as covariates and is stratified by baseline use of antipsychotics. Time to event endpoints will be analysed using Cox proportional hazard model and change from baseline endpoints will be analysed using the restricted maximum likelihood (REML) based mixed effects model with repeated measurements (MMRM).			

Trial Protocol

Proprietary confidential information © 2018 Boehringer Ingelheim International GmbH or one or more of its affiliated companies

FLOW CHART

Trial Periods	Screening Period	Randomized Treatment Period																							Completed Patients	Early D/C Option 1	Early D/C Options 2-4	Follow-up Period			

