- 14 The Columbia Suicide Severity Rating Scale (C-SSRS) Baseline/Screening version will be used at Visit 1 (Screening Visit). At other scheduled visits, the C-SSRS Since Last Visit version will be used. The screening eC-SSRS report must be reviewed by the investigator/qualified rater for validity prior to randomization.
- 15 The PANSS should also be administered at the time conversion to psychosis is diagnosed.
- 16 To confirm eligibility prior to start of the study treatment.
- 17 The first dose administration must be done on Day 1 at the site after all baseline assessments are completed.
- 18 Patients have the option of identifying an informant to provide ratings for the Schizophrenia Cognition Rating Scale (SCoRS). In person ratings are preferred whenever possible. However, if the informant is not available for in person ratings, telephone interview is acceptable.
- 19 The study staff must utilize the Interactive Response Technology (IRT) for entering the patient into the system for screening, randomisation, and study medication allocation and tracking.
- 20 Psychosis events after randomisation are Outcome Events. See [Section 5.3.6.3](#).
- 21 The NAPLS risk calculator score will be calculated and data entered by [REDACTED].
- 22 Patients who have prematurely discontinued study drug and have not continued making regular visits (in person or phone) must have Vital Status collected approximately one year after the patient was randomized.

TABLE OF CONTENTS

TITLE PAGE	1
CLINICAL TRIAL PROTOCOL SYNOPSIS	2
FLOW CHART	6
TABLE OF CONTENTS	9
ABBREVIATIONS	13
1. INTRODUCTION	16
1.1 MEDICAL BACKGROUND	16
1.2 DRUG PROFILE	18
2. RATIONALE, OBJECTIVES, AND BENEFIT - RISK ASSESSMENT	21
2.1 RATIONALE FOR PERFORMING THE TRIAL	21
2.2 TRIAL OBJECTIVES	22
2.3 BENEFIT - RISK ASSESSMENT	22
3. DESCRIPTION OF DESIGN AND TRIAL POPULATION	25
3.1 OVERALL TRIAL DESIGN AND PLAN	25
3.1.1 Administrative structure of the trial	26
3.2 DISCUSSION OF TRIAL DESIGN, INCLUDING THE CHOICE OF CONTROL GROUP(S)	27
3.3 SELECTION OF TRIAL POPULATION	27
3.3.1 Main diagnosis for trial entry	28
3.3.2 Inclusion criteria	29
3.3.3 Exclusion criteria	30
3.3.4 Removal of patients from therapy or assessments	31
3.3.4.1 Removal of individual patients	31
3.3.4.2 Discontinuation of the trial by the sponsor	33
4. TREATMENTS	34
4.1 INVESTIGATIONAL TREATMENTS	34
4.1.1 Identity of the Investigational Medicinal Products	34
4.1.2 Selection of dose in the trial	35

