5. VARIABLES AND THEIR ASSESSMENT

5.1 TRIAL ENDPOINTS

5.1.1 Primary Endpoint

The primary endpoint is time to remission from APS within a 52 week timeframe.

Per DSM-V, the proposed diagnostic criteria for APS are:

- A. At least one of the following of symptoms is present in attenuated form, with relatively intact reality testing and is of sufficient severity or frequency to warrant clinical attention:
 - Delusions
 - Hallucinations
 - Disorganized speech.
- B. Symptom(s) must have been present at least once per week in the last 1 month
- C. Symptom(s) must have begun or worsened in the past year
- D. Symptom(s) is sufficiently distressing and disabling to the individual to warrant clinical attention
- E. Symptom(s) is not better explained by another mental disorder, including: Depressive or bipolar disorder with psychotic features and is not attributable to physiological effects of a substance or another medical condition
- F. Criteria for any psychotic disorder have never been met.

A diagnosis of APS is defined by the presence of recent attenuated positive symptoms that meet ALL of 5 criteria: sufficient **severity** (criterion A), sufficient **frequency** (criterion B), **recency** of onset or worsening (criterion C), associated with sufficient distress or disability to warrant clinical attention (“**warrant attention** criterion,” criterion D), and not likely due to another disorder (“**attribution** criterion,” criterion E).

A patient in remission is defined as someone who no longer meets the severity criterion.

[figure not shown]
Remission from APS is defined as a score of <3 on all of the P1-P5 Positive Symptom items of the SOPS and maintained until the end of treatment.

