5.2 ASSESSMENT OF EFFICACY

Remission of APS, conversion to psychosis, functional capacity, cognitive function, and disease state will be measured by the batteries and questionnaires listed below:

The Structured Interview of Psychosis-Risk Syndromes (SIPS) is a structured interview for diagnosing a clinical high risk (CHR) syndrome for psychosis and cases of first episode psychosis [R16-0681]. It contains a severity rating scale (Scale Of Prodromal Symptoms, or SOPS), a well-anchored Global Assessment of Functioning (GAF) [R16-0594], the DSM-5 schizotypal personality disorder checklist, a brief assessment of the family history of psychosis, the Criteria Of Psychosis-risk Syndromes (COPS) and Presence Of Psychosis Scale (POPS) and DSM-5 Attenuated Psychosis Syndrome criterion sets.

The **SOPS**, contained within the SIPS, assesses Positive, Negative, Disorganization and General symptoms. It is administered as a semi-structured interview with 19 rating scales measuring severity and change of prodromal symptoms. Each item is scored from 0-6. The positive symptoms are scaled from 0 (absent) to 6 (severe and psychotic). The remaining items are scaled from 0 (absent) to 6 (extreme). The 19 rating scales are each independently anchored.

The Positive scale is used to make a diagnosis of attenuated psychosis syndrome (APS) and conversion to psychosis. To meet criteria for APS, a patient must at some point have rated level “3”, “4”, or “5” on at least one of the P1-P5 Positive Symptom items of the SOPS. The symptom(s) must have occurred at the then-current intensity level at an average frequency of at least once per week in the past month, and must not have been likely due to another disorder. The Negative, Disorganization and General domains are used to assess the severity of the diagnosis [\[R15-1441\]](#).

Conversion to psychosis and time to conversion will be adjudicated by the Central Rating Committee after review of video-taped SOPS interview. Adjudication will take into account information provided by patients, informants, and medical records when available.

Schizophrenia Cognition Rating Scale (SCoRS) will be used to evaluate everyday functional capacity.

The SCoRS is a 20-item interview-based assessment of cognitive deficits and the degree to which they affect day-to-day functions. It collects information from a patient interview, interview with an informant (if available), and the administering clinician.

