The HVLT-R measures verbal learning. The patient is asked to recall words from a list of 12 words read orally by the Rater. There are three learning trials with each administration. Delayed recall and recognition will not be administered. The HVLT-R score is the total number of words correctly recalled across the three trials.

NAPLS Risk Calculator uses an algorithm designed to predict individualized risk of psychosis in clinical high-risk patients using demographic, clinical, neurocognitive, and psychosocial predictor variables. The web-based risk calculator generates a score representing the probability of transition to psychosis within the next 12 months. The predictor variables used in this study are:

- Age
- Brief Assessment of Cognition in Schizophrenia: Symbol Coding (BACS SC)
- Hopkins Verbal Learning Test-Revised (HVLT-R)
- SIPS items P1 and P2 (unusual thought content and suspiciousness)

- Global Functioning: Social (assessment of decline in social functioning in the past year)

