7.3.1 Primary endpoint analyses

The primary endpoint is the time to remission from APS as defined in [Section 5.1.1](#).

The equality of the hazard rates will be tested by the Wald test for the treatment effect in a stratified Cox proportional hazards model at the two-sided 10% significance level. The model includes the treatment effect and NAPLS risk score as covariates and is stratified by baseline use of antipsychotic medication. Breslow's method for handling ties will be used.

The same stratified Cox proportional hazards model will be used to estimate the hazard ratio of BI 409306 vs. placebo and the asymptotic 90% Wald confidence interval. A hazard ratio of more than one favors BI 409306. The analysis will be implemented using █® PROC PHREG. Cox proportional hazard model assumptions will be verified.

[figure not shown]
The primary analysis will be performed on the FAS for the on treatment period. The date of remission will be the visit date on which the patient taking the assessment meets the remission criteria. The time to remission is defined to be the start of treatment until remission is achieved. Although patients who discontinue study medication will be followed until the end of the trial for the primary endpoint, the data collected after treatment discontinuation will only be used for a sensitivity analysis. Patients who are lost-to-follow up will be censored for the primary endpoint at the time of their last known SOPS assessment. Patients who begin taking a new prescription or increase in dose of ongoing antipsychotics will be considered as not eligible for remission. Such patients will be censored at the start of new prescription or increase of dose of ongoing antipsychotics. Further details regarding these analyses will be included in the TSAP.

The following sensitivity analyses will be performed: (1) on the primary endpoint that includes only patients from the TS during the time of the full follow-up period and (2) excluding patients who were recruited from the enriched population prior to amendment 3.

Subgroup analyses are planned and will be pre-specified in the TSAP.

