7.3.2 Secondary endpoint analyses

Time to event endpoints will be analysed using Cox proportional hazard model as described for the primary endpoint analysis. All change from baseline endpoints specified in [Section 5.1.2](#) will be analysed using the restricted maximum likelihood (REML) based mixed effects model with repeated measurements (MMRM). The model will include the fixed, categorical effects of treatment, visit, treatment by visit interaction, and NAPLS risk score strata, and baseline use of antipsychotic medication, as well as the continuous fixed covariates of baseline score and baseline-by-visit interaction. The unstructured covariance structure will be used to model the within-patient errors. If this analysis fails to converge, compound symmetry covariance structure might be used. The Kenward-Roger approximation will be used to estimate the denominator degrees of freedom. Analyses will be implemented using █® PROC MIXED. The primary treatment comparisons will be between the placebo and BI 409306 with respect to the mean change from baseline. Adjusted mean change from baseline as well as treatment contrasts will be presented together with the 95% confidence intervals.

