6.7 BASELINE, TIME WINDOWS AND CALCULATED VISITS

For all efficacy endpoints, “baseline” is defined as the assessments done at Visit 2, prior to administration of first dose. If this value is not available, the latest measurement before the first time drug administration (at screening (Visit 1), or an unscheduled visit) will be used.

For demographics, medical history, ECG, concomitant antipsychotic medication, AEs, concomitant therapies and vital signs, Visit 1 (screening) will be considered as “baseline”.

Visit will be labelled according to the flow chart in the protocol: Visit 1 (for screening), Visit 2 (randomization and start of treatment), Visits 3-23, End of Treatment (EOT), Follow Up (FU) (28 days after Visit 23 for completed patients; 28 days after EOT for early discontinued patients). Planned and actual test days will be calculated relative to the beginning of study as indicated in the following table.

Table 6.7: 1 Visit calculation relative to study start

Visit	Relative to study start	
	Planned test day (every 14 days)	Actual test day
2	1	1
3	8	Visit 3 date – first dose date +1
4	15	Visit 4 date – first dose date +1
5	22	Visit 5 date – first dose date +1
Etc...
23	365	Visit 23 date – first dose date +1
EOT	Visit 23 + (7 days)	EOT – first dose date + 1
FU	Visit 23 + 28 days	FU date – first dose date + 1

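### The primary Cox model omits baseline SOPS P1–P5 severity, although it is already rated before first dose; adding it is a cheap improvement, not the repair of an error

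*Protocol*

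**What the plan says.** - **Model.** Protocol 7.3.1: "The model includes the treatment effect and NAPLS risk score as covariates and is stratified by baseline use of antipsychotic medication". The treatment effect is tested by a Wald test at two-sided 10%. SAP 7.4, as far as it can be read, gives the hypotheses and no covariate list. The sensitivity analyses in SAP 7.4.1 change the follow-up period or the patient set, not the model.
- **Endpoint.** Protocol 5.1.1: "Remission from APS is defined as a score of <3 on all of the P1-P5 Positive Symptom items of the SOPS", sustained to the end of treatment. SAP 5.1 agrees.
- **Entry.** Protocol 5.2 requires a rating of 3, 4 or 5 "on at least one of the P1-P5 Positive Symptom items of the SOPS". Patients can therefore start with one item at 3 or with several at 5.
- **Timing.** The Flow Chart schedules SOPS from Visit 2, and its footnote 17 says: "The first dose administration must be done on Day 1 at the site after all baseline assessments are completed". Under SAP 6.7 the efficacy baseline "is defined as the assessments done at Visit 2, prior to administration of first dose". If the Visit 2 value is missing, the latest earlier pre-dose value is used.
- **Secondary endpoints.** For change from baseline, the mixed model in Protocol 7.3.2 contains "NAPLS risk score strata, and baseline use of antipsychotic medication, as well as the continuous fixed covariates of baseline score". SAP 7.5.2 also adjusts for the baseline score.
- **NAPLS.** By Protocol 5.2 the calculator predicts transition to psychosis from age, two cognitive tests, items P1 and P2, and decline in social functioning. Items P3 to P5 are not in it.
- **Achieved size.** SAP section 4 says recruitment left the trial much smaller than planned, and gives no number.

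**The concern.** Remission is the same as a maximum P1–P5 score below 3. A patient with one item at 3 has to fall by one point on one item; a patient with several items at 5 has to fall by three points on each. That starting distance is measured before treatment and is a natural candidate predictor of the endpoint, but the primary model uses it only through the share of P1 and P2 inside NAPLS. The change-from-baseline secondaries do adjust for their own baseline.

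Two things are at stake. If severity is prognostic, leaving it out gives up some power. And a chance imbalance in severity between the arms passes into the hazard ratio except for the part that NAPLS absorbs.

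**Working it through.** **1. The plan's own figure (Protocol 7.7).** Inputs: remission 40% against 57% by 52 weeks, 133 events, two-sided alpha 0.10, 1:1 allocation.
- Hazard ratio = ln(1 − 0.57) / ln(1 − 0.40) = (−0.844) / (−0.511) = 1.652, as stated.
- Power = Φ(√(133/4) × ln 1.652 − 1.645) = Φ(5.766 × 0.502 − 1.645) = Φ(1.25) = 89.4%. Allowing for the interim look (0.01 spent at 67% information) it is again 89.4%; the plan states 89.3%.
- Exponential remission with 20% dropout gives 132.1 expected events, against 133 stated.

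The design counts on no covariate gain, so it stands whether or not the term is added.

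**2. Power with and without the term.** Prognostic strength is not in the documents, so it is assumed over a range. Two simulations used a stratified Cox Wald test with Breslow ties, rates held at 40%/57%, 20% dropout, an assumed visit grid, an assumed 25% on antipsychotics, no interim, and NAPLS in both models. Severity was a standard normal variable. Its correlation with NAPLS was 0.3 or 0.6 in A (4,000 trials per scenario). In B (1,500 per scenario) it was 0 or 0.6 at N=300 and 0.6 at N=100 and 50. B used log hazard per SD of 0, 0.3, 0.5 and 0.8, that is 1.0-, 1.35-, 1.65- and 2.23-fold.

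| Simulation | N | Not prognostic | Weak | Moderate | Strong |
|---|---|---|---|---|---|
| A (1.25, 1.5, 2.0-fold) | 300 | −0.5 to +0.1 | +0.3 to +0.5 | +1.6 to +2.4 | +3.4 to +4.5 |
| B (1.35, 1.65, 2.23-fold) | 300 | −0.6 to +0.4 | +0.9 to +1.0 | +2.3 to +2.7 | +4.1 to +6.2 |
| B | 100 (assumed) | −0.5 | +0.3 | +1.6 | +5.8 |
| B | 50 (assumed) | −0.5 | +1.4 | +1.9 | +6.2 |

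Entries are changes in power, in percentage points. The Monte Carlo SE of the differences in A is 0.1 to 0.4. In B the SE of each power at N=300 is about 0.8, so the small entries are close to noise. Power without the term is 86–92% at N=300, 47–54% at N=100 and 28–34% at N=50.

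**3. Type I error at N=300.** A, at 1.5-fold, two-sided: 8.4–9.3% without and 8.4–9.0% with the term (nominal 10%). B, at 1.65-fold, upper tail: 4.4–4.8% without and 4.7–4.8% with (nominal 5%). No inflation is seen. It was not simulated at N=100 or 50, though every fit there converged.

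**4. Which severity score.** An item-level check used two assumed P1–P5 distributions and 3,000 trials per scenario (SE 0.2 to 0.5 points).
- Maximum item score, hazard driven by the maximum: +0.5 to +0.8, +1.4 to +2.0 and +4.3 to +4.5 points at 1.25-, 1.5- and 2.0-fold.
- Maximum item score, hazard driven by points above 2 summed over items: +0.3, +1.2 to +1.4 and +2.0 to +2.5.
- P1–P5 total, over all scenarios: −0.1 to +2.9.

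**5. Chance imbalance.** Take a one-standard-error difference between arms in the part of severity that NAPLS does not explain. It equals (2/√N) × √(1 − ρ²) SD, and the SE of the log hazard ratio is 2/√events. Hence

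shift/SE = √(events/N) × √(1 − ρ²) × ln(fold).

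With 133/300 and 1.5-fold: 0.666 × 0.405 = 0.270. Multiplying by 0.954 (ρ = 0.3) or 0.8 (ρ = 0.6) gives 0.26 or 0.22. At 1.25-fold the range is 0.12–0.14, and at 2.0-fold 0.37–0.44. With the event fraction fixed, N cancels.

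At 1.5-fold, a result at z = 1.645 (p = 0.10) moves to z = 1.86–1.90 (p about 0.06) or to z = 1.39–1.43 (p = 0.15–0.17).

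**The case against.** The strongest reply is that this is a design preference. The test is valid, the power holds, and the plan already adjusts for one prespecified score and stratifies by antipsychotic use. The benefit rests on an input that the documents do not contain and may be zero. The power figures in step 2 use an idealised normal covariate, whereas the maximum is a coarse integer, for which step 4 shows smaller gains when it is not the true driver. The simulations do not model the requirement that remission be sustained, or censoring at psychosis. The choice between maximum and total is not settled by the documents. The final SAP is dated 21 May 2021, it cut analyses because the sample was small, and an unblinded interim was planned.

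Most of this stands and limits the size of the claim. It does not remove it: the term uses data already collected, shows no alpha inflation at N=300, and costs about half a power point if severity is irrelevant.

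Three stronger readings are tempting and not supported.
- *The primary analysis is biased or underpowered.* Randomisation keeps the test valid, and step 1 reproduces the power.
- *Dozens of patients are wasted.* In A at 2.0-fold the squared ratio of mean z is 1.16 to 1.22, worth 300 × 0.16 to 0.22 = 48 to 66 patients. That strength is an assumption.
- *NAPLS and the antipsychotic stratum are inconsistently defined.* The synopsis has "categorized NAPLS risk score as covariates and is stratified by baseline use of antipsychotics", Protocol 7.3.2 speaks of strata and SAP 7.5.2 lists NAPLS among the categorical effects. Protocol 7.3.1 merely omits the form, and blacked-out SAP text may hold the cut-points. The Visit 1 baseline for antipsychotics in SAP 6.7 can be read as serving descriptive summaries, and using it for the stratum changed simulated power by only −0.2 to +0.2 points. Both are wording clarifications.

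**Conclusion.** The point holds as a low-cost improvement. The readable plan has no baseline P1–P5 severity term in the primary model, although the endpoint is a threshold on those items and they are rated before dosing. The gain is roughly 0 to +6 power points at N=300, and similar at an assumed N of 50 to 100, which matters because the sample fell well short. It also protects against chance imbalance: a shift of 0.22 to 0.26 SE for a one-standard-error imbalance at an assumed 1.5-fold hazard per SD. Both figures depend on prognostic strength that the documents do not state. If severity does not predict remission, there is no gain. A blacked-out SAP section could already contain a supportive severity analysis.

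**What to change.** Before unblinding, write one model statement in Protocol 7.3.1 and SAP 7.4: treatment, NAPLS risk score and one continuous Visit 2 pre-dose SOPS P1–P5 severity score, stratified by antipsychotic use as randomised. The maximum item score matches the endpoint definition; a P1–P5 sum is acceptable if fixed in advance. Use one term, not five items, given the small sample. Keep the current treatment-plus-NAPLS model as a sensitivity analysis.

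The cost is small. No new data are needed, and SAP 6.7 already covers a missing Visit 2 value. The downsides are:
- one extra parameter;
- a linearity assumption, which can be checked;
- a hazard ratio conditional on severity, to be labelled so (in B at 1.65-fold the median estimate moves from about 1.66 to about 1.72 for the same 40%/57% rates);
- a late change, which must be dated and documented as made without access to unblinded results.

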		1*	2	3	4	5	6	7	8	9	10	11	12	13	14	15	16	17	18	19	20	21	22	23				F/U***	End of Study****		
Visit	1*	2	3	4	5	6	7	8	9	10	11	12	13	14	15	16	17	18	19	20	21	22	23	EOT**	EOT**	EOT**					
Study week	-4	0	1	2	3	4	5	6	9	12	15	18	21	24	27	30	33	36	39	42	45	48	52	52				56			
Study day	-28	1	8	15	22	29	36	43	64	85	106	127	148	169	190	211	232	253	274	295	316	337	365	365				393			
Visit window in days	-28 to -7	N/A	+/-1	+/-2	+/-1	+/-2	+/-1	+/-2	+/-3	+/-3	+/-3	+/-3	+/-3	+/-3	+/-3	+/-3	+/-3	+/-3	+/-3	+/-3	+/-3	+/-3	+/-3	+/-3				+/-3			
Informed consent ¹		X																													
Demographics		X																													
Medical history		X																													
Physical examination		X									X			X			X			X			X				X				
Vital signs		X	X	X	X	X	X	X	X	X	X	X	X	X	X	X	X	X	X	X	X	X	X	X	X	X	X				
Height		X											X										X				X				
Weight		X	X								X			X			X						X			X	X	X			
Pregnancy test (urine; females only) ²		X	X	X	X	X	X	X	X	X	X	X	X	X	X	X	X	X	X	X	X	X					X				
12 lead-ECG ³		X								X	X	X	X	X	X	X	X	X	X	X	X	X	X					X			
Safety laboratory tests (urine/blood) ⁴		X	X							X	X	X	X	X	X	X	X	X	X	X	X	X	X	X	X	X	X	X			
Substance Use Assessment ⁵		X																													
Urine drug screen		X	X							X			X			X			X			X					X				
Salivary Cortisol ⁶			X							X			X									X					X				
BDNF, Inflammatory Cytokines Sampling ⁶			X							X			X									X					X				
Pharmacogenomic sampling		X ⁷	X ⁸																												
Optional DNA biobanking (requires separate ICF) ⁹			X																												
SIPS ¹⁰		X																					X					X			
SOPS ¹⁰			X	X	X	X	X	X	X	X	X	X	X	X	X	X	X	X	X	X	X	X	X	X	X	X	X	X			
Global Functioning: Social		X								X			X			X			X			X					X			X	
BACS-SC & HVLT-R ¹¹		X								X			X			X			X			X					X			X	
BAC App ¹²			X								X			X			X			X			X				X			X	
Phone Visit ¹³				X	X	X	X	X	X	X	X	X	X	X	X	X	X	X	X	X	X	X	X	X	X	X	X				

Trial Protocol

Proprietary confidential information © 2018 Boehringer Ingelheim International GmbH or one or more of its affiliated companies

FLOW CHART (cont.)

Trial Periods	Screening Period	Randomized Treatment Period																							Completed Patients	Early D/C Option 1	Early D/C Options 2-4	Follow-up Period
		2	3	4	5	6	7	8	9	10	11	12	13	14	15	16	17	18	19	20	21	22	23	EOT**	EOT**	EOT**	F/U***	End of Study****
Visit	1*	2	3	4	5	6	7	8	9	10	11	12	13	14	15	16	17	18	19	20	21	22	23					
Study week	-4	0	1	2	3	4	5	6	9	12	15	18	21	24	27	30	33	36	39	42	45	48	52					56

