- 4 Routine laboratory tests are hematology, chemistry, coagulation, urinalysis, and endocrine parameters as described in [Table 5.3.3:1](#). Patients should be fasting for at least 8 hours prior to the blood samples collected at Visit 2 and Visit 23/EOT.
- 5 Patients will be asked whether they have ever or are currently using/consuming tobacco, alcohol and cannabis.
- 6 Saliva and blood samples should be collected at approximately the same time of the day at each visit. Baseline samples must be collected prior to first dose. Patients will be instructed to refrain from caffeine, alcohol, dairy products, and nonprescription medications the evening before and the morning of saliva sampling.
- 7 One blood sample will be taken at screening for genotyping of CYP2C19 from all patients taking medication known to be strong or moderate inhibitors of CYP1A2.
- 8 One blood sample for the analysis of pre-specified genes will be collected at Visit 2 from all patients.
- 9 Collection of a sample for DNA biobanking is optional (See [Section 5.5](#) for more details). Participating patients are required to give informed consent specifically for biobanking. DNA biobanking requires only one blood sample to be taken, preferably at Visit 2 (Randomisation). However, collection at later visits is permitted as long as the informed consent for biobanking remains valid.
- 10 The Structured Interview for Psychosis-Risk Syndromes (SIPS) and Scale of Prodromal Symptoms (SOPS) interviews will be video-taped for review by [REDACTED].
- 11 The BACS SC and HVLT-R are paper assessments. The paper BACS SC at Visit 23 is a different version than the BACS SC in the BAC App that is also completed at Visit 23.
- 12 Patients who do not speak English will take the pen-and-paper Brief Assessment of Cognition Schizophrenia (BACS) available in their native language.
- 13 Interim phone visits are scheduled to assess the overall status of the patient, check compliance, and to collect new AE and concomitant medication information. If symptom worsening is suspected, an unscheduled in-clinic visit should be scheduled to administer SOPS. See [Section 6.2.2](#). Columns are shaded in grey in the [Flow Chart](#) to indicate phone visits.

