7.7 DETERMINATION OF SAMPLE SIZE

Remission rate of the population diagnosed with APS and without intervention was assumed to be 40% ([R16-0991](#)) by 52 weeks. The rate of remission for BI 409306 was assumed to be 57% by 52 weeks. This will lead to a hazard ratio of 1.652.

Other study considerations are:

- Two-sided alpha = 0.10
- Dropout = 20% after one year
- Interim analysis checking for early efficacy using user-defined alpha-spending boundary of 0.01 at the 67% information point

Table 7.7: 1 Power calculations for sample size (for both arms combined) of 300 for various remission rates for BI 409306 with fixed placebo group aggregate first remission rate prediction of 40% by 52 weeks

Remission Rate for Placebo	Remission Rate for BI 409306	Hazard Ratio	Risk Ratio	Power for N=300	# Events needed in total
40%	52%	1.437	1.300	64.9%	126
40%	55%	1.563	1.375	81.5%	130
40%	57%	1.652	1.425	89.3%	133
40%	59%	1.745	1.475	94.4%	136
40%	61%	1.843	1.525	97.4%	139

[Table 7.7: 1](#) displays the power achieved for 300 total randomized patients given a group aggregate first remission rate of 40% for placebo with two-sided $\alpha = 0.10$ and a user-defined

alpha spending boundary at interim analysis of $\alpha=0.01$ (two-sided). Group remission rates for BI 409306 treatment of 52%, 55%, 57%, 59% and 61% are considered. Total number of events needed to achieve the power reported is also shown.

Given remission rates of 40% for patients treated with placebo and 57% for patients treated with BI 409306, the risk ratio is 1.425 (implying that patients treated with BI 409306 will have 42.5% more chance of achieving remission of APS compared to placebo). A sample size of 300 (or 150 per group) was selected as the most logical for establishing proof of concept based on the risk / benefit considerations noted above. In addition this was the sample size used in the previous protocol and is kept the same. This translates to 89% power. The type I error was selected to be 10% since this is a phase II study meant to provide an understanding of the effectiveness of the drug without being too strict as in a confirmatory setting.

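### Breslow's tie method in the primary Cox model pulls the remission hazard ratio slightly toward 1, because remissions are dated to visits; Efron's method avoids this at almost no cost

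*Protocol*

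**What the plan says.** Protocol 7.3.1 sets out a stratified Cox model with a Wald test at the two-sided 10% level: "The model includes the treatment effect and NAPLS risk score as covariates and is stratified by baseline use of antipsychotic medication". For tied times it states that Breslow's "method for handling ties will be used". On dating the event it says: "The date of remission will be the visit date on which the patient taking the assessment meets the remission criteria". Time runs from the start of treatment.

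The flow chart has a row headed "Visit window in days". It allows 1 or 2 days either side up to week 6 and 3 days either side from week 9. Footnote 13 separates clinic from phone visits: "Interim phone visits are scheduled to assess the overall status of the patient", and "If symptom worsening is suspected, an unscheduled in-clinic visit should be scheduled to administer SOPS".

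SAP 7.4, as supplied, restates the hypotheses but names no tie method, so the protocol's choice stands. SAP Table 6.7: 1 counts actual test days from the first dose date.

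**The concern.** Remission is assessed only when SOPS is given, so event times cluster at scheduled visits. When several patients remit on the same study day, Breslow's likelihood keeps all of them in the risk set for each of those events. The fitted log hazard ratio is then too close to 0, and more so as the share of the risk set failing together grows. Efron's method removes most of this error, and the exact method avoids the approximation. A bias toward no effect in the primary estimate, with some lost power, would have no offsetting benefit. The question is how large it is under this trial's schedule.

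**Working it through.** **1. The plan's own figure.** Protocol 7.7 gives 40% vs 57% remission at 52 weeks, 20% dropout, N=300, "Two-sided alpha = 0.10", hazard ratio 1.652, 133 events and 89.3% power.
- HR = ln(1 − 0.57)/ln(1 − 0.40) = 0.8440/0.5108 = 1.652.
- Expected events with exponential remission and dropout times: 132.1.
- Schoenfeld: μ = √(133 × 0.25) × ln 1.652 = 5.766 × 0.502 = 2.894. Power = Φ(2.894 − 1.645) = 89.4%. A two-look calculation with the 0.01 interim boundary also gives 89.4%.

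The stated figure reproduces, and no tie method enters it.

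**2. Number of SOPS dates.** The extracted flow chart marks SOPS in nearly every column, but it marks Phone Visit in nearly every column too, so neither row settles the count. Three points lead to 11:
- Global amendment 2 added ECG and laboratory tests at Visits 8, 12, 16, 20 and 22, which implies clinic attendance.
- Visits 10, 14, 18 and 23 are weeks 12, 24, 36 and 52.
- Visits 4 and 6 (weeks 2 and 4) have the 2-day window, unlike the 1-day visits around them.

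The upper limit from the extracted chart is 21.

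**3. Density of ties.** 133/11 ≈ 12 remissions per visit. Spread over a 7-day window that is about 12.1/7 = 1.7 per day, before splitting by stratum. In simulation with 11 visits, 131 events fell on 80 distinct stratum-times when dates were spread (1.6 each), and on 21 when every visit was on its nominal day (6.2 each).

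**4. The two likelihoods.** Take d tied events, risk-set sum S, and sum D over the tied patients. Breslow uses the denominator S^d. Efron uses ∏(S − (k/d)D) for k = 0,…,d−1.

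**5. Simulation.** Three paired simulations fitted both methods to the same data: A with 800 trials per scenario, B and C with 2,000 each. All rows are N=300, true HR 1.652.

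| Visits, dates | Run | HR Breslow / Efron | Power Breslow / Efron |
|---|---|---|---|
| 21, spread | B | 1.645 / 1.647 | 87.6% / 87.7% |
| 11, spread | A | 1.645 / 1.649 | 90.3% / 90.4% |
| 11, spread | B | 1.639 / 1.643 | 87.2% / 87.4% |
| 11, spread | C | 1.650 / 1.654 | 87.4% / 87.6% |
| 11, half on nominal day | A | 1.642 / 1.652 | 87.3% / 87.9% |
| 11, half on nominal day | C | 1.647 / 1.657 | 87.5% / 87.7% |
| 11, all on nominal day | A | 1.625 / 1.651 | 86.9% / 88.8% |
| 11, all on nominal day | B | 1.618 / 1.644 | 85.8% / 87.0% |
| 11, all on nominal day | C | 1.632 / 1.659 | 88.8% / 90.0% |

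Compare within rows only. Each power in B has a Monte Carlo standard error of about 0.7 point, and each paired difference about 0.1 to 0.4 point. In B with 11 visits, the ratio r of the Breslow to the Efron log HR is 0.995 (spread) and 0.968 (nominal day), and the standard errors are almost identical (0.1796 for both when spread).

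**6. Check by formula.** With equal standard errors, Breslow's z is r times Efron's, so its power is Φ(μ − 1.645/r).
- r = 0.995: Φ(2.894 − 1.653) = 89.3%, a loss of about 0.2 point from 89.4%.
- r = 0.968: Φ(2.894 − 1.699) = 88.4%, a loss of about 1.0 point.

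**7. Type I error.** In run B at HR = 1, two-sided rejection was 9.75% (Breslow) vs 9.85% (Efron) with dates spread, and 10.3% vs 11.35% with all on the nominal day. The Monte Carlo standard error is √(0.1 × 0.9/2000) = 0.7 point. Breslow is within one standard error of 10% in both cases. Efron's 11.35% is two above it, so this run does not show that the whole worst-case gain comes free.

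**8. Smaller trial.** SAP section 4 says the sample was much smaller than intended but gives no number. For assumed sizes, Efron gains 0.2 point (spread) or 1.3 points (nominal day) at N=50, and 2.3 points (nominal day) at N=100. The log HR ratio at N=50 is 0.995 and 0.970, about the same as at N=300.

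**The case against.** The strongest reply is that the protocol's own rules break most ties. It uses actual visit dates, counts days from first dose, allows windows of up to 3 days either side, and stratifies the model. With dates spread, the difference is in the third decimal of the hazard ratio. That stands, and it is why the point is minor. Even spread is the favourable extreme, though. Every inferred clinic day is a whole number of weeks after Day 1, and Protocol 6.1 ties later visits back to the randomisation date, so some clustering on nominal days is plausible. The documents do not give the actual spread.

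A reader might infer that SOPS is given at only a few visits and that power suffers seriously. The documents do not support this. In run B a 3-point loss appeared only with 4 visits all on the exact day, which is not this schedule.

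A reader might also extend the point to time to psychosis, because Protocol 7.3.2 reuses the same model. Protocol 5.1.2 and SAP 5.2.2 date that onset by the rater's best estimate or by the start or increase of antipsychotic medication. The visit-dating argument therefore does not apply there.

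That a smaller trial has fewer ties is true, but the proportional shrinkage barely changes.

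**Conclusion.** The point holds as a small, one-directional inefficiency in the primary time-to-remission model. At N=300 with 11 SOPS visits, Breslow shrinks the log hazard ratio by about 0.5% (0.1 to 0.2 points of power) if dates spread evenly over the windows, and by up to about 3% (1 to 2 points) if all visits fall on the nominal day. Across the N=300 scenarios of run C, Efron alone rejected in 43 trials and Breslow alone in none.

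It would be wrong to conclude that the test is invalid or the stated power mistaken: Breslow's null rejection rate is close to 10%, and the 89.3% reproduces without any tie method.

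Runs B and C assume exponential remission times, 30% baseline antipsychotic use and no NAPLS effect, and they do not model the requirement that remission be maintained. The 11 visits are inferred.

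**What to change.** Before unblinding, specify TIES=EFRON (or TIES=EXACT, feasible at this size) in Protocol 7.3.1 and SAP 7.4 for the primary time-to-remission model and its sensitivity analyses, and document the change. The cost is one option in the PHREG call and one line of text. The documents do not show whether unblinding has taken place. If it has, keep Breslow as the primary analysis and report Efron as a sensitivity analysis only.
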